Subjects not eligible for thrombectomy (criterion 3.I) receive less iodine contrast agent and radiation exposure compared to patients undergoing thrombectomy, where iodine is used to navigate during the procedure under X-ray image guidance. Investigational DE-CBCT of these subjects on day 1 imposes varying extent of residual iodine intracranially (from previous standard of care imaging). However, these subjects typically show very relevant imaging features, as hyperacute ischemic changes are challenging yet crucial to visualize. Moreover, DE-CBCT imaging potentially enables iodine removal/suppression. If still hospitalized day 2, an additional DE-CBCT enables diagnostic information about stroke progression.

Subjects that have undergone thrombectomy (inclusion criteria 3.II) will be included one day after admission (day 2), when most of the iodine typically has been filtered out by the kidneys. An absolute GFR (aGFR) and non-renal risk factors for CI-AKI will be assessed before administering iodine contrast agent. These measures will ensure that the risks associated with iodine contrast agents will be minimized.

Similar to above, subjects with a verified intracranial hemorrhage (inclusion criteria 3.III) will be imaged without and with iodine contrast agent day one after assessment of aGFR and non-renal risk factors.

If the subject is deemed inappropriate to receive iodine contrast agent, only imaging without iodine contrast agent will be done. In addition to above, other individual or healthcare aspects may select subjects to undergo only imaging without injection of iodine contrast agent.

6. Study Design

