8.2. Sample size justification

Statistical analyses will be performed by Karolinska University Hospital. This is a prospective, open label single centre study. A diagnostic study using DE-CBCT on confirmed acute ischemic or hemorrhagic stroke has not been done before. The sample size estimations aims to prove diagnostic quality non-inferiority compared to CT according to performance goals below.

The sample size for the primary endpoint is trait-based, using ten [10] ASPECTS regions for each subject. To evaluate the diagnostic accuracy of DE-CBCT compared to CT, it is estimated that a sample size of 137 is required to render a power of 90% (target accuracy of 0.90, performance goal lower boundary of 0.80, one-sided alpha of 0.025). For this endpoint, a minimum sample size of 14 subjects is required.

The first secondary endpoint (vessel tree visibility) is also trait-based, using eleven [11] arterial regions for each subject. To evaluate the proportion of regions rated equal or superior to CT, it is estimated that a sample size of 126 is required to render a power of 80% (target proportion of 0.90, performance goal lower boundary of 0.80, one-sided alpha of 0.0125, adjusted for multiple secondary endpoints). For this endpoint, a minimum sample size of 12 subjects is required.

IGT Systems	Clinical Research Protocol Next Generation X-ray Imaging System (NEXIS)	Doc ID: XCY612-130814 Rev: 01 Page 34 of 57
-------------	----------------------------------------------------------------------------	---------------------------------------------------

The second secondary endpoint is defined as diagnostic accuracy to determine the presence of intracranial hemorrhage, comparing DE-CBCT to CT (reference). The endpoint is subject-based and it is estimated that a sample size of 20 is required to render a power greater than 95% (target accuracy of 0.9999, performance goal lower boundary of 0.80, one-sided alpha of 0.0125, adjusted for multiple secondary endpoints). The sample size includes both subjects with hemorrhage and negative controls, preferably with 0.5 hemorrhage prevalence, with a threshold of at least a third of our subjects to have an intracranial hemorrhage. For this endpoint, a minimum sample size of 20 is required.

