In total, the minimum sample size required is 20 subjects, of which two-thirds have ischemia, one-third have intracranial hemorrhage, and at least half must have done a contrast enhanced DE-CBCT. Our estimated necessary sample size is 29 subjects, taking algorithm optimization and potential invalid data into account.

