8.3. Statistical methods

All variables will be summarized by descriptive statistics. The statistics for continuous variables includes mean, median, standard deviation, 95% confidence interval for the means, and the number of observations. For categorical variables, number of events, event rate, and 95% confidence interval for the event rate will be presented.

For categorical variables, the Fisher's Exact or chi-squared test will be used. For numerical variables, Student's t-test will be applied for image quality parameters such as signal-to-noise ratio (SNR) and contrast-to-noise ratio (CNR). For ordinal rank variables concerning radiologist interpretation, the Wilcoxon test will be used. The decision to use non-parametric or parametric tests will be based on the result from Shapiro-Wilk test as well as the distribution of the data on a P-P plot.

Receiver operating characteristic (ROC) curves will be constructed and accuracy as well as area under the curve (AUC) will be used to assess image diagnostic performance, where applicable. Sensitivity, specificity, negative and positive predictive value will be assessed with optimal cut off, where applicable. The DeLong test will be applied when comparing ROC curves. The Kappa coefficient will be used to evaluate interrater and within-observer agreement, where applicable. Additional statistical methods may be used in accordance with relevant literature (33). A biostatistician is involved in planning and executing the statistical analyses.

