8.6. Primary objective

8.6.1. Ischemic stroke diagnostic accuracy

Endpoint

Accuracy of DE-CBCT ASPECTS to determine the extent and localization of ischemic stroke changes in brain tissue, using neCT ASPECTS as the reference standard.

Applicable subjects

Subjects diagnosed with ischemic stroke on CT.

Data

- ASPECTS
 - Left / Right
 - 1 to 10
 - Location - L, C, IC, I, M1, M2, M3, M4, M5, M6

Analysis

Images are evaluated by radiologists using neCT as reference standard and the ASPECTS diagnostic accuracy is defined.

Hypothesis:

$$H_0: \pi_1 \leq 0.80$$

$$H_1: \pi_1 > 0.80$$

Where π_1 is the observed ASPECTS accuracy and 0.80 is the performance goal.

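### Section 8.2 counts regions as independent and no clustered test is named: if regions within a subject correlate, the stated alpha is unprotected, and holding it costs the stated power at the minimum 14 and 12 subjects

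*Combined protocol and SAP*

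**What the plan says.** Section 8.2 sizes the primary endpoint by region: "The sample size for the primary endpoint is trait-based, using ten [10] ASPECTS regions for each subject". It asks for 137 regions (accuracy 0.90 against a goal of 0.80, one-sided alpha 0.025, power 90%) and converts them to 14 subjects. For vessel visibility, "The first secondary endpoint (vessel tree visibility) is also trait-based, using eleven [11] arterial regions for each subject". Here it asks for 126 regions (same two proportions, one-sided alpha 0.0125, power 80%) and converts them to 12 subjects.

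The overall minimum is 20 subjects. The planned number is higher for two stated reasons only: "Our estimated necessary sample size is 29 subjects, taking algorithm optimization and potential invalid data into account".

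On analysis, section 8.6.1 gives the hypotheses against 0.80 and then says: "Images are evaluated by radiologists using neCT as reference standard and the ASPECTS diagnostic accuracy is defined". Section 8.7.1 is worded in the same way. Neither names a test. Section 8.3 offers general tools: "For categorical variables, the Fisher's Exact or chi-squared test will be used", and "For categorical variables, number of events, event rate, and 95% confidence interval for the event rate will be presented". It also leaves room for further methods from the literature without naming any. Section 8.1 assigns three independent neuroradiologists, but no section says how their calls on one region become a single result.

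**The concern.** The ten or eleven regions of one subject come from one scan, one reconstruction and the same readers. A subject whose images are poor, or unusually clear, will tend to be read wrongly or rightly in several regions at once. Section 5.5 names one further subject-level factor, for group 3.I: "Investigational DE-CBCT of these subjects on day 1 imposes varying extent of residual iodine intracranially".

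With positive correlation, 140 regions from 14 subjects carry less information than 140 independent regions. A test that ignores this passes a device whose true accuracy is only 0.80 more often than the stated alpha allows. A test that respects it has less power than stated. Section 8.2 says the sizing is meant to prove non-inferiority, with formal hypotheses and a multiplicity-adjusted alpha, so the error rate of these two tests matters even in a proof of concept. Because no test is named, the choice could also be made after the data are seen, and the same data could pass one test and fail another.

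**Working it through.** **Step 1: reproduce the plan.** Inputs from 8.2: p0 = 0.80, p1 = 0.90, alpha 0.025 and 0.0125, power 90% and 80%. Find the smallest n with a cut-off c such that P(X ≥ c | n, p0) ≤ alpha and P(X ≥ c | n, p1) reaches the target, X binomial.

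- Primary: n = 137, c = 119, size 2.45%, power 91.0%.
- Vessel: n = 126, c = 111, size 1.18%, power 80.9%.

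These are the plan's figures. Then 137/10 = 13.7, rounded to 14 subjects, and 126/11 = 11.45, rounded to 12. The design effect used is therefore 1.

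**Step 2: model the clustering.** The documents give no ICC, so I assume 0.05 to 0.30. Subject i has accuracy p_i drawn from Beta(ps, (1−p)s) with s = (1−ICC)/ICC. The correct calls in that subject are Binomial(m, p_i), m = 10 or 11. The total is the exact convolution over subjects. All regions share one mean accuracy.

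"Unadjusted" keeps the binomial cut-off: 122/140, 116/132, 163/190, 144/165 and 272/319 for the five designs below. "Alpha held" raises the cut-off until the size is at or below alpha at that ICC. For 14×10 it becomes 124, 125, 127 and 129 of 140; for 12×11 it becomes 118, 120, 122 and 125 of 132. This treats the ICC as known, so it is a guide and not a usable test.

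The planned designs assume that all 29 subjects are usable and that the mix stated for the minimum also applies to 29: 29 × 2/3 = 19.3, so 19 ischemic; 29/2 = 14.5, so 15 contrast scans as the least allowed. The case with contrast in all 29 is added.

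| Subjects × regions | Quantity, % (stated) | ICC 0.05 | 0.10 | 0.20 | 0.30 |
|---|---|---|---|---|---|
| 14×10 (minimum) | type I, unadjusted (2.5) | 4.1 | 6.5 | 11.1 | 14.8 |
| | power, unadjusted (90) | 85 | 82 | 79 | 76 |
| | power, alpha held (90) | 73 | 64 | 50 | 39 |
| 12×11 (minimum) | type I, unadjusted (1.25) | 3.2 | 5.5 | 10.1 | 14.0 |
| | power, unadjusted (80) | 79 | 76 | 73 | 71 |
| | power, alpha held (80) | 64 | 47 | 36 | 22 |
| 19×10 (planned) | type I, unadjusted (2.5) | 5.2 | 7.8 | 12.5 | 16.2 |
| | power, unadjusted (90) | 95 | 92 | 88 | 86 |
| | power, alpha held (90) | 90 | 79 | 61 | 51 |
| 15×11 (planned, least contrast) | type I, unadjusted (1.25) | 2.8 | 4.9 | 9.2 | 12.9 |
| | power, unadjusted (80) | 85 | 82 | 78 | 76 |
| | power, alpha held (80) | 75 | 60 | 42 | 33 |
| 29×11 (planned, all contrast) | type I, unadjusted (1.25) | 2.7 | 4.8 | 8.9 | 12.5 |
| | power, alpha held (80) | 97 | 89 | 74 | 59 |

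At ICC 0 the whole-subject minimums give size 1.85% and power 89.4% (14×10), and size 1.21% and power 83.2% (12×11).

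**Step 3: hand check.** Design effect D = 1 + (m−1)·ICC. For 14×10 at ICC 0.05, D = 1.45 and the effective n is 140/1.45 = 96.6. Power ≈ Φ[(0.10·√96.6 − 1.96·0.40)/0.30] = Φ(0.66) ≈ 75%, close to the 73% above.

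**Step 4: a test that could be run.** The Korn-Graubard bound uses t on subjects minus 1 df, with the effective n capped at the number of regions (simulated, 200,000 runs per cell). Results at ICC 0 / 0.05 / 0.10 / 0.20 / 0.30:

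- 14×10: type I 1.2 / 1.9 / 2.4 / 2.9 / 3.3%; power 81 / 64 / 53 / 40 / 33%.
- 12×11: type I 0.5 / 1.0 / 1.3 / 1.9 / 2.4%; power 64 / 46 / 37 / 28 / 24%.

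At its nominal level it therefore exceeds the limit at an ICC of about 0.20 (primary) and 0.10 (vessel). An uncorrected t-test on subject proportions is worse: 3.6 to 7.1% and 2.1 to 5.6% over ICC 0 to 0.30.

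**The case against.** **The ICC is assumed.** This stands: the size of the effect is conditional. The model also gives every region the same accuracy. Fixed differences between regions reduce the variance. As an illustration, 8 of 11 vessels at 0.90 and 3 at 0.533 average 0.80, with variance (8×0.09 + 3×0.249)/11 = 0.133 against 0.16, a ratio of 0.83. Clustering then has to make up a factor of 1/0.83 = 1.2 = 1 + 10·ICC, so the vessel alpha is passed near an ICC of 0.02 instead of about 0.0015. The direction at 0.05 and above is unchanged.

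**The planned 29 gives a margin.** A reader might infer that alpha and power both fail at the planned size. The table does not support that. With all subjects usable, unadjusted power stays at or above target up to an ICC of about 0.10. But that margin is already assigned to algorithm optimization and invalid data, and it does nothing for alpha.

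**Residual iodine.** A reader might take it as affecting every subject. Section 5.5 ties it to day-1 scans in group 3.I, says that most iodine has typically cleared by day 2 in group 3.II, and notes that the technique may suppress it. The general argument rests on the shared scan, reconstruction and readers.

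**The plan limits correlation and leaves room.** Subjects with motion-degraded images are replaced (6.6.2). Primary reads are stripped of acquisition details and separated in time (8.1). Section 8 refers departures from its methods to a Statistical Analysis Plan, and 8.3 says a biostatistician is involved. These reduce the problem or permit a clustered method, but none specifies one.

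**Readers.** A reader might infer that the plan pools three readers' calls as independent data. Nothing says so: 8.2 counts one observation per region. The combination rule is simply not stated.

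**Conclusion.** The point holds as a gap in the sizing and in the named analysis. The figures 137 and 126 are correct under independence, and independence is assumed without being stated or justified.

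Over an assumed ICC of 0.05 to 0.30 with a common accuracy across regions, an unadjusted test runs at 4.1 to 14.8% instead of 2.5%, and at 3.2 to 14.0% instead of 1.25%. A larger sample does not repair this. At the stated minimums, power with alpha held is 73 to 39% and 64 to 22%, against 90% and 80%. At planned numbers with everyone usable, power with alpha held is about 90% (19×10) and 75% (15×11) at ICC 0.05, and lower above that; with contrast in all 29, vessel power still exceeds 80% at ICC 0.10.

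The documents do not show that the plan has committed to an unadjusted test, since it names none, nor that 29 subjects must be too few. This should be settled before the analysis, because it decides what a pass on the primary endpoint means.

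**What to change.** 1. In 8.3, 8.6.1 and 8.7.1, prespecify one subject-clustered, one-sided lower bound or test against 0.80 with a small-sample correction. Korn-Graubard with t on subjects minus 1 df is one candidate. Set its nominal level by simulation over a stated ICC range that includes 0, so that type I error stays at or below 0.025 and 0.0125; left unadjusted, Korn-Graubard does not meet this over the whole range. State that the three readers' calls on a region are not counted as extra independent observations.

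2. In 8.2, replace the single 90% and 80% power figures with a power table for that test over the same ICC range, at the minimum (14 and 12) and the expected subject numbers.

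The cost is wording, a short simulation and a less favourable stated power; no extra subjects or reads are needed. The price is paid even if regions are in fact independent: at ICC 0, Korn-Graubard at its nominal level has 81% and 64% power at the minimums, against 89% and 83% for the exact binomial test, and lowering its level would reduce that further. Whether to enrol more subjects in response to the table is a separate decision for the sponsor.

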8.7.2. Intracranial hemorrhage detection accuracy

Endpoint (2nd Secondary endpoint)

Accuracy of DE-CBCT to determine the presence of intracranial hemorrhage using neCT as the reference standard.

Applicable subjects

All subjects in the study.

Data

- Intracranial hemorrhage
 - Yes / No

Analysis

Images are evaluated by radiologists using neCT as reference standard and the hemorrhage detection accuracy is defined.

Hypothesis:

$$\begin{aligned} H_0: \pi_3 &\leq 0.80 \\ H_1: \pi_3 &> 0.80 \end{aligned}$$

Where π_3 is the observed intracranial hemorrhage accuracy and 0.80 is the performance goal.

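### The hemorrhage endpoint tolerates no error at 20 to 29 subjects, so its stated power rests on a target of 0.9999; Holm in place of the fixed 0.0125 split is a free but partial gain

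*Combined protocol and SAP*

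**What the plan says.** Section 8.2 gives both secondary endpoints a one-sided alpha of 0.0125. For hemorrhage it states "The endpoint is subject-based and it is estimated that a sample size of 20 is required to render a power greater than 95" percent, under "target accuracy of 0.9999, performance goal lower boundary of 0.80, one-sided alpha of 0.0125, adjusted for multiple secondary endpoints". For vessel visibility it asks for 126 regions, with 80% power at a true proportion of 0.90 against the same goal of 0.80. The multiplicity method is not named; 0.0125 equals 0.025/2, which is an equal split.

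The overall minimum is 20 subjects, and the section adds: "Our estimated necessary sample size is 29 subjects, taking algorithm optimization and potential invalid data into account". Section 8.7.2 applies the hemorrhage endpoint to "All subjects in the study" and sets the hypothesis as accuracy of at most 0.80 against accuracy above 0.80. Its analysis text is "Images are evaluated by radiologists using neCT as reference standard and the hemorrhage detection accuracy is defined".

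Section 8.3 names Fisher's exact or chi-squared for categorical variables, and no one-sample test. It also says that a "95% confidence interval for the event rate will be presented". Neither section gives the pass rule as a number of errors, or power at any accuracy other than 0.9999.

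**The concern.** With about 20 binary results, a high performance goal and a halved alpha, the test has very few possible cut-offs. If the only passing result is a perfect one, power is simply the probability of no error, which falls quickly once true accuracy is even slightly below 1. It also falls as more subjects are enrolled within the planned range. Someone reading only the headline figure would take this endpoint as nearly certain to succeed.

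Two smaller matters follow from the same choice. A fixed equal split gives up rejections that a step-down procedure would allow at the same error rate. And a 95% interval reported beside a one-sided 0.0125 test can sit above 0.80 when the test has failed, so the study report could appear to say two things at once.

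**Working it through.** **Inputs.** Goal 0.80, target 0.9999, alpha 0.0125 one-sided, n = 20 minimum and 29 planned (sections 8.2 and 8.7.2); vessel visibility 126 regions, 0.90 against 0.80, alpha 0.0125 (section 8.2). Assumptions of this check: an exact binomial test; one call per subject; accuracies of 0.95 to 0.99 chosen for illustration, since the documents give no source for any value.

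**Reproducing the plan.** The smallest p-value possible with n subjects is 0.8^n.
- 0.8^19 = 0.0144, above 0.0125: no result can pass at 19.
- 0.8^20 = 0.0115, below 0.0125: 20 of 20 passes.
- Power at the target is 0.9999^20 = 0.998, which agrees with the stated figure of more than 95%.

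So 20 is the smallest size at which the exact test can pass at all, which supports the assumption about the test.

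**Pass rule.** With one error, p = 0.8^n + n × 0.2 × 0.8^(n−1).

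| n | p, zero errors | p, one error |
|---|---|---|
| 20 | 0.0115 | 0.0692 |
| 25 | 0.0038 | 0.0274 |
| 26 | 0.0030 | 0.0227 |
| 27 | 0.0024 | 0.0187 |
| 28 | 0.0019 | 0.0155 |
| 29 | 0.0015 | 0.0128 |
| 30 | 0.0012 | 0.0105 |

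The one-error p-value falls steadily with n and stays above 0.0125 up to 29. Zero errors is the only pass from 20 to 29; one error first passes at 30.

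**Power.** Under this rule power is t^n for true accuracy t. For 95% power, t must be at least 0.95^(1/20) = 0.9974 at n = 20, or 0.95^(1/29) = 0.9982 at n = 29.

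| True accuracy (assumed) | n = 20 | n = 29 |
|---|---|---|
| 0.99 | 0.818 | 0.747 |
| 0.98 | 0.668 | 0.557 |
| 0.95 | 0.358 | 0.226 |

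**Holm.** The smaller of the two secondary p-values is tested at 0.0125 and, if that rejects, the other at 0.025.
- Hemorrhage, n = 20 to 25: the one-error p-value is 0.0274 or more, so the rule stays at zero errors and Holm adds nothing.
- Hemorrhage, n = 26 to 29: the one-error p-value lies between 0.0125 and 0.025, so one error passes if the vessel test has passed at 0.0125.
- At n = 29 and accuracy 0.98, P(zero errors) = 0.557 and P(one error) = 29 × 0.02 × 0.98^28 = 0.329. With vessel power 0.809 and independent endpoints, power is 0.557 + 0.329 × 0.809 = 0.823. The ceiling, if the vessel test always passes, is 0.557 + 0.329 = 0.886.
- Vessel visibility, 126 regions treated as independent: the cut-off is 111 at 0.0125 (power 0.809) and 110 at 0.025 (power 0.875). The second figure is reached only when hemorrhage has passed, so it is an upper limit.

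**Intervals.** With one error, the Clopper-Pearson 95% lower limit is 0.804, 0.810, 0.817 and 0.822 at n = 26, 27, 28 and 29. All exceed 0.80 although the 0.0125 test fails. The 97.5% two-sided interval at n = 29 has lower limit 0.799, in line with the test.

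**The case against.** A reader might infer that the stated power is wrong or concealed. It is neither: it follows from the target of 0.9999, which stands in the same sentence. The accuracies of 0.95 to 0.99 used here have no source in the documents, so the lower power figures are a sensitivity range and not a prediction.

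A reader might also infer that Holm rescues the hemorrhage endpoint. At the required minimum of 20 it does nothing for it. The gain begins at 26 evaluable subjects, and section 8.2 presents 29 as including an allowance for algorithm optimization and invalid data, so 26 or more evaluable subjects is not assured. The vessel figures also treat regions within a subject as independent, as the plan does; clustering would lower vessel power and with it the gain for hemorrhage.

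The pass rule depends on the test. An uncorrected score test would fail even 20 of 20 (p = 0.0127), a mid-p test would allow one error from n = 27, and a Wald test would allow one already at n = 20. This stands as a limit on certainty, but it also shows why the test should be named.

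The 95% intervals in section 8.3 are descriptive and are nowhere made the decision rule, so there is no contradiction in the plan itself, only a possible mismatch in reporting.

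Finally, testing the secondary endpoints only after the primary passes might look like a natural companion change. It would be a trade-off that lowers secondary power, and nothing here depends on it.

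**Conclusion.** The point holds in a limited form. Assuming an exact binomial test, the hemorrhage endpoint fails on a single subject-level error at any size from 20 to 29, and power above 95% requires a true accuracy of at least 0.9974 at 20 subjects. The stated power is correct but fragile: at an assumed accuracy of 0.98 it is 67% at 20 subjects and 56% at 29.

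The fixed split can be improved at no cost, but the benefit is partial. Vessel power rises from 0.81 to at most 0.87. Hemorrhage power at 29 subjects and accuracy 0.98 rises from 0.56 to about 0.82 if the endpoints are independent. At 20 to 25 subjects hemorrhage gains nothing. The interval mismatch is confined to exactly one error at 26 to 29 subjects.

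The documents do not say how the three readers' calls become one result per subject, so it does not follow that one reader's mistake would decide the endpoint.

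**What to change.** 1. In section 8.2, replace the fixed 0.0125 for each secondary endpoint by Holm over the two at one-sided 0.025. The error rate across the pair is unchanged and Holm never rejects less than the split, so there is no statistical cost.
2. In section 8.3, report the secondary intervals at the level of the test actually applied: 97.5% two-sided, or 95% where Holm tests at 0.025.
3. In sections 8.2 and 8.7.2, name the exact binomial test and state that, at 0.0125, zero errors is the only pass from 20 to 29 subjects. Beside the figure for 0.9999, show power over 0.95 to 0.99. The cost is a less favourable stated power.

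All three are changes of wording and need no further subjects.

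### At the stated minimum of 20 subjects, the hemorrhage share in section 8.2 and the 14 ischemic subjects needed for the primary endpoint do not fit together unless some subjects count in both groups

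*Combined protocol and SAP*

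**What the plan says.** **Primary endpoint.** Section 8.2: "The sample size for the primary endpoint is trait-based, using ten [10] ASPECTS regions for each subject". With "target accuracy of 0.90, performance goal lower boundary of 0.80, one-sided alpha of 0.025", "it is estimated that a sample size of 137 is required to render a power of 90" per cent. In subjects: "For this endpoint, a minimum sample size of 14 subjects is required". Section 8.6.1 defines the applicable subjects as "Subjects diagnosed with ischemic stroke on CT".

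**Second secondary endpoint (hemorrhage detection).** Section 8.2 gives 20 subjects for power above 95%, assuming accuracy 0.9999 against a goal of 0.80 at one-sided 0.0125. The wanted mix is "preferably with 0.5 hemorrhage prevalence, with a threshold of at least a third of our subjects to have an intracranial hemorrhage". Section 8.7.2 tests one pooled accuracy over every subject in the study.

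**Summary of the sample size.** Section 8.2 concludes that "the minimum sample size required is 20 subjects, of which two-thirds have ischemia, one-third have intracranial hemorrhage", and plans 29 subjects to allow for tuning of the algorithms and for unusable data. The Summary and section 6.6.1 repeat both figures.

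**The concern.** Ischemic subjects are the only ones who contribute to the primary analysis, so each subject recruited for the hemorrhage share is one fewer for the primary test, unless that subject also has an ischemic stroke. Section 8.2 gives three statements about the mix: at least 14 ischemic subjects, hemorrhage at one-third or preferably one-half, and a two-thirds to one-third split of 20. It does not say which prevails when they disagree. The primary is the only endpoint sized at 90% power, so the question is how much of that power survives at each mix, and what the preference for one-half buys in return.

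**Working it through.** **Inputs (section 8.2).** Primary: p1 = 0.90, p0 = 0.80, one-sided alpha 0.025, 10 regions per subject, regions treated as independent. Hemorrhage: p1 = 0.9999, p0 = 0.80, one-sided alpha 0.0125, n = 20. Assumption for steps 2 to 4: no subject counts in both groups.

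**1. Reproduce the plan's figures.** Exact one-sample binomial: take the smallest c with P(X ≥ c | n, p0) ≤ alpha; power is P(X ≥ c | n, p1).
- Primary: 137 is the smallest n with at least 90% power (c = 119, attained alpha 0.0245, power 91.0%). The normal approximation, n = [(z(1−alpha)·√(p0(1−p0)) + z(power)·√(p1(1−p1)))/(p1−p0)]², gives 136.5, so also 137. At 10 regions each, 13.7 rounds up to 14 subjects.
- First secondary: "it is estimated that a sample size of 126 is required to render a power of 80" per cent. The exact method gives 126 (power 80.9%); the normal approximation gives 132.03, so 133. The plan therefore appears to use the exact method.
- Hemorrhage: c = 20 of 20, 0.8^20 = 0.0115, power 0.9999^20 = 99.8%, consistent with the stated figure above 95%.

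**2. The split at 20 subjects.** Two-thirds of 20 is 13.3 and one-third is 6.7. In whole subjects, 13 and 7 meets the hemorrhage floor but misses 14 ischemic. A split of 14 and 6 meets the primary minimum but puts hemorrhage at 6/20 = 30%, below one-third. No whole-number split of 20 meets both.

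**3. Primary power by number of ischemic subjects.**

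| Ischemic subjects | Regions | Pass mark | Exact power | Normal approximation |
|---|---|---|---|---|
| 10 (0.5 mix of 20) | 100 | 89 | 70.3% | 76.4% |
| 13 (one-third floor at 20) | 130 | 114 | 84.7% | 88.2% |
| 14 | 140 | 122 | 89.4% | 90.8% |
| 15 | 150 | 130 | 92.8% | 92.9% |
| 19 | 190 | 163 | 97.6% | 97.6% |

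Exact power moves in steps, so 140 regions gives slightly less than 137. The value at 100 regions is at a low point: a pass mark of 88 would give 80.2%, but with alpha 0.0253, just over the limit.

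**4. The planned 29.** A 0.5 mix leaves 14 or 15 ischemic subjects (89.4% or 92.8%). It supplies 14 only down to 28 evaluable subjects (28/2 = 14), so one lost subject uses up the margin. At the one-third floor, 10 of 29 are hemorrhage and 19 ischemic (97.6%), and the total can fall to 21 (14 + 7) before the two minima collide.

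**5. What the 0.5 preference buys.** Pooled accuracy = prevalence × sensitivity + (1 − prevalence) × specificity. With both at 0.9999, accuracy is 0.9999 at any prevalence, so power at n = 20 stays at 99.8%. If sensitivity and specificity differ, prevalence can move power either way. With 0.90 and 0.95 (assumed), power is 25.2% at one-third and 21.0% at one-half; with 0.95 and 0.90 it is 17.5% and 21.0%. The benefit is descriptive: with no missed hemorrhage, the one-sided 97.5% lower bound for sensitivity is 0.025^(1/10) = 69% with 10 cases and 0.025^(1/7) = 59% with 7.

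**6. Overlap needed at 20.** To reach 14 ischemic subjects, 14 + 7 − 20 = 1 subject must count in both groups at the one-third floor, and 14 + 10 − 20 = 4 at the 0.5 mix.

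**The case against.** The strongest reply is that the 10-subject case is artificial. The 0.5 figure is only a preference, while the 14-subject minimum and the two-thirds share are stated requirements. Section 6.3 enrols consecutive eligible patients as the device is available, and no recruitment quota there applies the 0.5. The planned total is 29, and sections 6.6.1 and 6.6.2 replace withdrawn subjects and those with scans spoiled by movement. A reader might infer that the trial will run its primary test at 70% power. The documents do not support that: it requires the preference to override two stated minima at the smallest allowed total.

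Overlap is also possible. Section 8.7.2 scores hemorrhage yes or no in every subject, and section 8.8.3 provides for hemorrhagic transformation of ischemic stroke, so one subject may serve both endpoints. The section 8.2 summary, however, presents the groups as shares adding to one and states no rule for counting such subjects.

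A balanced mix is a defensible aim. Section 8.3 plans sensitivity and specificity where applicable, and balance keeps negatives from dominating pooled accuracy: calling every scan negative would score 67% at one-third prevalence and 50% at one-half. So the further inference that the preference is worthless also fails; it lacks value only for the power of the planned test under the plan's own assumption.

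What remains is that the figures conflict at 20 even without the preference, since the one-third floor alone leaves 13. At 29 with a 0.5 mix the margin is one subject. Section 8.1 uses the first cases to tune the reconstruction, without saying whether they leave the analysis or how many there are.

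**Conclusion.** The concern holds as an inconsistency in section 8.2, with a moderate effect at the floor and a larger one only if the preference is followed at small totals. At 20 subjects without overlap, the plan's own one-third floor gives 84.7% exact primary power (about 88% by the normal approximation) rather than 90%. The 0.5 preference would give 70.3% (about 76%). At 29 evaluable subjects and a 0.5 mix, power is essentially as planned, but almost none of the allowance for tuning and unusable cases is left.

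These results assume no subject in both groups and independent regions within a subject, as in the plan. Positive within-subject correlation would lower every primary power shown. With an assumed intraclass correlation of 0.05 to 0.2 and design effect 1 + 9 × ICC, the normal approximation gives 75% to 40% at 14 subjects and 56% to 27% at 10. That is a separate matter and does not change the ordering of the mixes.

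**What to change.** In section 8.2:

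1. State that at least 14 evaluable ischemic subjects take priority over the hemorrhage share.
2. Delete the 0.5 preference, or let it apply only once those 14 are assured, which without overlap means from 28 evaluable subjects.
3. Correct the minimum in one of three ways:
   - set it at 21 evaluable subjects, 14 ischemic and 7 with hemorrhage (primary 89.4% exact; hemorrhage test 0.9999^21 = 99.8%);
   - keep 20 and restate primary power as about 85% at 13 ischemic subjects;
   - keep 20 and state that subjects with hemorrhagic transformation count for both endpoints, with at least one such subject needed at the one-third floor.

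Repeat the change in the Summary and section 6.6.1. Deleting the preference alone would not be enough, because the one-third floor already leaves 13 ischemic subjects at 20.

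The cost is a few sentences. The 21-subject option raises the minimum by one but stays within the planned 29. The downside is fewer hemorrhage cases than under a 0.5 mix, hence a wider descriptive interval for hemorrhage sensitivity: a zero-miss lower bound of 59% with 7 cases instead of 69% with 10.
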